- time to first acute exacerbation of CRS, defined as a worsening of symptoms that requires escalation of treatment
- percent of subjects requiring rescue medication after Week 4

- change from baseline to Week 12 and Week 24/ET in the PSQI global and component scores
- percent of subjects indicating improvement on the PGIC at Week 4 and Week 24/ET
- severity of depression at Week 24/ET as measured by QIDS
- change from baseline to Week 24/ET for:
  - the MCS of the SF36v2
  - the PCS of the SF36v2
  - SF-36v2 individual domains
  - QIDS total score
  - SIT scores
  - EQ-5D VAS and dimensions
  - SF-6D derived scores
- comparison of health economic measures during the double-blind treatment phase related to CRS:
  - percent of subjects indicating that they are willing to consider sinus surgery at baseline and Week 24/ET
  - percent of subjects who meet the minimal objective criteria for surgical intervention (as defined in [Section 7.3](#)) at baseline and Week 24/ET
  - percent of subjects approved for surgery who no longer elect to undergo a surgery Week 24/ET
  - number and percentage of missed work days and the percentage of productive hours lost while at work from the HPQ
- change from baseline to Week 24/ET in SNOT-22 total score in subjects from both studies OPN-FLU-CS-3205 and OPN-FLU-CS-3206 who report using an intranasal, topically acting nasal steroid for the treatment of CRS within 30 days of Visit 1
- change from baseline to Week 24/ET the Global PSQI Score from studies OPN-FLU-CS-3205 and OPN-FLU-CS-3206

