### 5.6.2 Rescue Medication

Use of rescue medication for CRS symptoms is not allowed during the single-blind run-in or before the Week 4 visit of the double-blind treatment phase. Subjects will be allowed to use over-the-counter non-sedating antihistamine (eg, cetirizine, levocetirizine, desloratadine) at the label recommended, usual dose per day as rescue medication following the Week 4 visit.

Other concomitant medications are allowed, if not specially listed below as prohibited.

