- Zinreich modification of the Lund-Mackay Staging System total score, scores for ethmoids and maxillary sinuses combined, and for each sinus pair (e.g., ethmoids, maxillary, frontal, and sphenoid)
- Zinreich modification of the Lund-Mackay Staging System score for the worst sinus between maxillary and ethmoid sinuses
- SF36v2 MCS Domain, PCS Domain, and individual health domains
- QIDS total score
- SIT scores

Change from baseline to Week 24/ET for EQ-5D VAS scores will be analyzed with the ANCOVA model described above; EQ-5D dimensions will be summarized. Further details will be provided in the SAP.

The percent of subjects considered improved (ie, subjects with ratings of 1 [very much improved] or 2 [much improved]) based on the PGIC at weeks 4 and 24/ET will be analyzed with a logistic regression MMRM model; further details will be provided in the SAP.

The Kaplan-Meier method and log-rank test will be used to estimate and compare the distributions of time to first exacerbation between OPN-375 and placebo.

The following endpoints will be analyzed using a logistic regression model; further details will be provided in the SAP:

- QIDS Severity of Depression at Week 24/ET
- The percent of subjects requiring rescue medication from Week 4 to Week 12; subjects without use of any rescue medication during the period Week 4 to Week 12 will be referred to as rescue-free subjects.
- The percentage of subjects who meet the eligibility criteria for surgery at Week 24

The percent of subjects indicating that they are willing to consider sinus surgery at baseline and Week 24, and the percent of subjects approved for surgery who no longer elect to undergo a surgery Week 24 within each treatment group will be compared with McNemar's test.

The total number of times a subject requires rescue medication after Week 4 to Week 12 will be tabulated. Rescue free subjects will be assigned a zero ('0') for this tabulation. This endpoint will be analyzed with an ANCOVA model based on ranks.

Change from baseline to Week 24/ET for SF-6D will be summarized as described in the SAP.

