2 INTRODUCTION

This Statistical Analysis Plan (SAP) has been developed after review of Sponsor Protocol OPN-FLU-CS-3205 (Amendment 6.0, dated 07 January 2022) and the corresponding electronic case report form (eCRF). This SAP describes the statistical methods to be used for the analysis and reporting of all efficacy and safety data collected during the conduct of Protocol OPN-FLU-CS-3205.

This SAP supersedes the statistical considerations identified in original Protocol OPN-FLU-CS-3205, as well as the SAP dated 19 April 2021, which is based on Protocol Amendment 4.1 and is the basis for the IASAP dated 8 June 2021. This SAP contains all changes incorporated into Protocol Amendment 6.0, and there are no deviations from this amendment presented in this SAP. If additional analyses are performed to supplement the planned analyses described in this SAP they will be identified as such in the Clinical Study Report (CSR).

This SAP is being written with consideration of the recommendations outlined in the following International Conference on Harmonization (ICH) Guidance for Industry documents:

- E9: Statistical Principles for Clinical Trials
- E9-R1 Addendum: Estimands and Sensitivity Analysis
- ICH E3: Structure and Content of Clinical Study Reports

This SAP also incorporates the recent FDA Guidance regarding the COVID-19 Public Health Emergency (PHE):

- FDA Guidance on the Conduct of Clinical Trials of Medical Products during COVID-19 Public Health Emergency: Guidance for Industry, Investigators, and Institutional Review Boards, (11 May 2020)

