8.10 Rescue Medications

The incidence of rescue medication use during the placebo-run period will be presented in the Subject Listings.

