11 CHANGES FROM THE PROTOCOL

The following changes were made to this SAP post Protocol Amendment 6.0.

Section 3.3.3 and 3.4.3 (Objectives and Endpoints)

The following objectives and secondary endpoints were added:

- change from baseline to Week 24/ET in APOV in the ethmoid sinuses (APOV-E)
- change from baseline to Week 24/ET in APOV in the maxillary sinuses (APOV-M)
- change from baseline to Week 24/ET in APOV in the ethmoid sinuses (APOV-E) for CRS with NP and without NP sub-groups and in subjects with and without previous sinus surgery
- change from baseline to Week 24/ET in APOV in the maxillary sinuses (APOV-M) for CRS with NP and without NP sub-groups and in subjects with and without previous sinus surgery
- change from baseline in the volume of the nasal cavity opacified

The following objective and secondary endpoint was removed:

- percent of subjects requiring rescue medication after Week 4

Section 7.2 Sensitivity Analyses

- Section 7.2.3 Added an Observed Cases Sensitivity Analysis

Section 7.5.3 and Section 9.3.2 (Percentage of Opacified Volume)

- Clarified the definition of WPOV, WPOV-E, WPOV-M and the corresponding endpoints
- Added the definition of APOV-E and APOV-M and the corresponding endpoints

Section 7.5.4 and Section 9.3.6 (Qualitative CT Scan Assessment)

- Clarified the definition of WZLM and the corresponding endpoints

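### The SAP performs neither of the protocol's two analyses of double-blind rescue use, and its list of changes names only one of them

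*Protocol*

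**What the plan says.** Protocol 2.3 and 3.2.1.3 list as a secondary objective and endpoint the "percent of subjects requiring rescue medication after Week 4". Protocol 9.6 assigns that endpoint, worded there as "The percent of subjects requiring rescue medication from Week 4 to Week 12", to a logistic regression whose details are left to the SAP. The same section adds a second measure: "The total number of times a subject requires rescue medication after Week 4 to Week 12 will be tabulated". Subjects who used none are scored zero, and "This endpoint will be analyzed with an ANCOVA model based on ranks". The count appears only in 9.6. Protocol 7.2 has each rescue dose recorded after the Week 4 visit through Week 12, and SAP 9.3.1 repeats that the diary captures this.

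SAP 11 states "The following objective and secondary endpoint was removed" and names the percent alone. SAP 2 says that "there are no deviations from this amendment presented in this SAP". SAP 8.10, the only section on rescue output, reads: "The incidence of rescue medication use during the placebo-run period will be presented in the Subject Listings". Protocol 5.6.2 says of the same period: "Use of rescue medication for CRS symptoms is not allowed during the single-blind run-in".

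**The concern.** The protocol leaves the details of the logistic regression to the SAP, and the SAP does not supply them. The count is in a worse position: the protocol requires its analysis, while the SAP neither performs it nor records that it was dropped. A programmer following the SAP produces no Week 4 to 12 rescue result. A reader who relies on SAP 2 would not know that one was due.

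Rescue use is an outcome in its own right, because a drug that works may show part of its benefit as less rescue. It also bears on the symptom scores that SAP 7.5.1 still analyses at Weeks 8 and 12. Antihistamine rescue is not an intercurrent event in SAP 7.1.2, so those scores are used as recorded. If rescue relieves symptoms and placebo subjects use more of it, the difference is diluted; if an active arm uses more, the difference is inflated. Without rescue use by arm, the reader cannot judge which applies.

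**Working it through.** The main check compares the two documents item by item; the plan has no figure of its own to reproduce here.

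| Item | Protocol, Amendment 6.0 | SAP |
|---|---|---|
| Percent of subjects using rescue | Objective (2.3), endpoint (3.2.1.3), logistic regression (9.6) | Absent from 3.3.3, 3.4.3 and 7.3 to 7.8; named as removed in 11, no reason |
| Number of times used | 9.6 only, where it is called an endpoint; ANCOVA on ranks | Absent; not mentioned in 11 |
| Data | Each dose recorded after the Week 4 visit through Week 12 (7.2) | Diary capture restated (9.3.1) |
| Rescue output | Two between-group analyses | Run-in listing (8.10) |
| Conformity | Not applicable | Section 2 claims no deviations; Section 11 lists several changes |

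**Tally.** Analyses planned in the protocol: 2. Present in the SAP: 0. Of the 2 missing, 1 is disclosed and 1 is not. SAP 11 files the removal under its objectives and endpoints sections. Its entries for Section 7.5 concern only opacified volume and CT staging, so nothing there covers the count.

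**Is rescue open throughout the Week 8 and Week 12 windows?** The Week 4 visit is nominally Day 28, with a window of plus or minus 7 days.

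- Latest in-window visit: 28 + 7 = Day 35.
- Week 8 window (SAP Table 9.1): Days 49 to 55. It starts 49 − 35 = 14 days after the latest access date.
- Week 12 window: Days 77 to 83. It starts 77 − 35 = 42 days after.

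For any subject seen within the visit window, rescue is therefore permitted on 7 of 7 days in both windows.

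**How large is the effect on those differences?** It would be roughly the between-arm difference in rescue use on the window days, multiplied by the effect of rescue on the score. The documents give neither input, nor how many days per week a user takes rescue. They also give no planned Week 8 or Week 12 difference to compare with. I therefore report no number.

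**Cost in comparisons if both analyses are restored.** Two endpoints x two doses = 4. Protocol 9.6 and SAP 7.5 also call for a combined-dose contrast against placebo in the secondary models: 2 endpoints x 1 = 2. The total is up to 4 + 2 = 6.

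**The case against.** The strongest reply is that this is an incomplete change log. The removal of the percent is disclosed in the section meant for such changes, and that section gives no reason for any of its entries. The count was never a listed objective or endpoint; it depends on the rescue-free definition inside the percent item, so dropping the parent may have been meant to drop the count too. Both analyses and the Week 8 and Week 12 scores lie outside the Type I error hierarchy and carry nominal p-values.

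Most of that stands and limits the weight of the point. It does not remove it. The wording in SAP 11 is singular and names one item, the protocol calls the count an endpoint with its own model, and SAP 2 is contradicted by SAP 11 whatever was intended. A line in the log would cure the inconsistency but would still leave rescue use by arm unreported.

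A second reply is that antihistamines will show up elsewhere. Protocol 5.6 puts all concomitant medication on the CRF, SAP 9.5.1 uses start and stop dates, and SAP 8.9 summarises by treatment group, class and preferred term. Because subjects had to be able to stop antihistamines at screening (Protocol 4.1), that table is a rough proxy. However, it counts a subject once per term, does not identify use as rescue, does not isolate Weeks 4 to 12, and gives no dose counts.

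A reader might go further and infer that the endpoint was dropped because of what the data showed. The documents do not support this: SAP 4.5 records that only blinded interim looks took place and that the unblinded one did not occur.

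**Conclusion.** The point holds as an inconsistency with a modest reporting consequence. Two protocol-specified analyses of double-blind rescue use are missing from the SAP, one disclosed without a reason and one not disclosed, against a statement that nothing deviates. As a result a secondary efficacy result goes unreported, and the nominal Week 8 and Week 12 composite-score differences are read without rescue use by arm.

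Two stronger readings should be resisted. One is that the Week 4 co-primary result is compromised. The omitted analyses do not enter the co-primary model or the testing sequence, and rescue is barred until the Week 4 visit. A visit earlier than nominal could leave some of Days 21 to 27 after access opened, but the documents give no visit timing or rescue use from which a bias could be shown. The other is that the Week 8 and Week 12 differences are biased by some stated amount. Direction and size both depend on rescue rates, frequency of use and rescue effect, none of which is documented.

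The finding itself rests on the text alone. The 7-of-7 exposure statement assumes that the Week 4 visit falls within its window.

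**What to change.** Reconcile Protocol 9.6, SAP 2 and SAP 11.

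1. **Preferred.** Restore both analyses in SAP 7.5, each dose against placebo, with nominal p-values. For any use, fit a logistic regression with the factors of the SAP's other logistic models (previous sinus surgery, polyp status, treatment). For the number of times, fit the ANCOVA on ranks that Protocol 9.6 states. Say how a subject whose diary stops before Week 12 is classed, because the protocol wording would count one with no recorded use as rescue-free. Report diary days by arm.
2. **Minimum.** Add a descriptive summary of rescue use by arm for Week 4 to Week 12, and within Days 49 to 55 and Days 77 to 83, the windows behind the Week 8 and Week 12 scores.
3. **If the tests stay out.** List both the percent and the count in SAP 11, with the reason, before unblinding.
4. **In every case.** Correct the no-deviations sentence in SAP 2.

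The cost is two model runs or a few lines of text, with no new data and no alpha. The downside is up to six more nominal comparisons, which must not be read as confirmatory. No change to the rescue rules is proposed.

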## 9.7 Subgroup Analyses

The co-primary endpoints will be analyzed according to the primary estimand, with the subgroups defined based on actual polyp and surgical status, for the following stratification subgroups:

1. Subjects with polyps versus without polyps at baseline
2. Subjects with prior sinus surgery versus without prior sinus surgery at baseline

In addition, the following secondary endpoints will be analyzed for the stratification groups, using the statistical models described in Section 9.6 for these endpoints; further detail on these statistical methods will be provided in the SAP:

- Change from baseline CSNS, other than the primary, and the individual daily nasal symptom scores that are components of the CSNS
- Change from baseline SNOT-22 total
- Change from baseline WPOV-E, WPOV-M, and WPOV
- Zinreich modification of Lund-MacKay Staging System score for the worst sinus between maxillary and ethmoid sinuses

## 9.8 Type I Error Control for Multiplicity

### 9.8.1 Co-primary Efficacy Endpoints

The primary hypotheses of this trial are that at least one OPN-375 dose group will be superior to the placebo group in both co-primary endpoints.

The familywise Type 1 error probability for the test of the primary hypothesis is  $\alpha=0.05$ . If the unblinded interim analysis occurs, then  $\alpha=0.0001$  will be spent on this interim analysis and the family-wise Type 1 error probability for the test of the primary hypothesis will be  $\alpha=0.0499$ .

Details of this IA and the approach to control for Alpha will be contained in the detailed in the Interim Analysis SAP (IASAP).

The strategy for strong, familywise control of the Type I error is based on closed testing procedure as follows.

1. Test each co-primary endpoint for OPN-375 high dose (372 µg) vs placebo: If  $p < 0.05$  for both endpoints, then proceed to test low dose comparison; otherwise, stop.
2. Test each co-primary endpoint for OPN-375 low dose (186 µg) vs placebo: If  $p < 0.05$  for both endpoints, then proceed to test key secondary endpoints; otherwise, stop.

There are two comparisons for each dose: OPN-375 high dose (372 µg) vs placebo and OPN-375 low dose (186 µg) vs placebo. The order of the testing is as follows:

1. OPN-375 372 µg versus placebo in the change from baseline in the 7-day average instantaneous AM CSNS at the end of Week 4
2. OPN-375 372 µg versus placebo in the APOV in the ethmoid and maxillary sinuses change from baseline to Week 24/ET
3. OPN-375 186 µg versus placebo in the change from baseline in the 7-day average instantaneous AM CSNS at the end of Week 4
4. OPN-375 186 µg versus placebo in the APOV in the ethmoid and maxillary sinuses change from baseline to Week 24/ET

### **9.8.2 Type I Error Control for Key Secondary Endpoints**

There are four planned comparisons among the two key secondary efficacy endpoints. These comparisons are defined based on pooled data from Study OPN-FLU-CS-3205 and Study OPN-FLU-CS-3206. Testing will continue based on closed testing procedure with  $\alpha=0.05$ , if both primary hypotheses are met, as follows:

1. OPN-375 372 µg versus placebo in change from baseline to Week 4 on CSNS score in subjects who were symptomatic at trial entry despite reported use of an intranasal steroid for treatment of CRS within 30 days of Visit 1
2. OPN-375 186 µg versus placebo in change from baseline to Week 4 on CSNS score in subjects who were symptomatic at trial entry despite reported use of an intranasal steroid for treatment of CRS within 30 days of Visit 1
3. OPN-375 372 µg versus placebo in the frequency of acute exacerbations of CRS over 24 weeks
4. OPN-375 186 µg versus placebo in the frequency of acute exacerbations of CRS over 24 weeks

## **9.9 Safety Analysis**

All safety summaries will be descriptive; no statistical inference procedures will be applied. All safety summaries will be presented by OPN-375 dose level 186 µg, 372 µg, and OPN-375 combined doses and placebo.

### **9.9.1 Adverse Events (AEs)**

All reported AEs will be coded using the Medical Dictionary for Regulatory Activities (MedDRA) version 20 or higher. Treatment-emergent AEs (TEAEs) are defined as AEs with onset dates on or after the start of double-blind study drug. The incidence of TEAEs during the study period will be tabulated by treatment group and body system (or System Organ Class [SOC] and preferred term) overall, by severity, and by relationship to study drug using subject counts and percent. Those AEs with missing onset dates or missing severity will be included as treatment-emergent. If an AE is reported more than once during the double-blind study phase, the greatest severity and the worst-case attribution will be used for presentation in tables.

Deaths, SAEs, and AEs causing discontinuation of study participation and /or study treatment will be tabulated by treatment group with subject counts and percent. Adverse events for individual subjects will be listed, along with information regarding onset, duration, severity, and relationship to study drug.

### **9.9.2 Other Safety Endpoints**

Baseline physical examination findings and clinical laboratory data will be summarized. Vital signs and weight will be summarized using descriptive statistics including mean values and change from baseline values, as well as numbers of subjects with values outside limits of the normal range at each time point.

Prior/concomitant medications will be coded using the World Health Organization (WHO) Drug Dictionary (WHODrug), Version December 2010 or later, and summarized by drug class with subject counts and percent.

## **9.10 Interim Analysis**

An interim analysis is planned for both co-primary endpoints in this study to evaluate the sample size assumptions as follows:

1. A blinded, pooled IA of co-primary endpoint change from baseline in the 7-day average instantaneous AM CSNS to assess the variance. This IA is planned to occur when approximately 50% of randomized subjects have reached Week 4 CSNS endpoint. Since subjects need only to have completed the CSNS endpoint assessment, the blinded IA of CSNS variance will occur first.
2. A blinded, pooled IA of co-primary endpoint change from baseline to Week 24/ET APOV to assess variance. This IA is planned to occur after approximately one-third of randomized subjects have completed the study (Week 24/ET). Based on the results of this blinded IA of APOV, an unblinded IA of APOV to assess the conditional probability of rejecting the null hypothesis at the end of the study, given the observed interim result (Conditional Power), will be considered according to the following decision criteria:
  - a. If  $SD \leq 29.7\%$ , (i.e. within 10% of target), then no unblinded IA will be performed.
  - b. If observed  $SD > 29.7\%$ , then perform unblinded IA at the earliest feasible time post the blinded IA. This unblinded IA will be performed by an independent, unblinded statistician not involved in the conduct of the study.

The complete details of this interim analysis is provided in the IASAP. In the event the unblinded IA occurs, a partial unblinding of specified data and personnel will occur. The plan,

procedures, and methods for this unblinded interim analysis are detailed in the IASAP as well.

Under the assumption that an unblinded IA will occur as planned, and assuming a non-binding futility boundary, the Type 1 error probability for the interim analysis is conservatively assumed to be  $\alpha < 0.0001$ ; therefore, the Type 1 error probability for the final analysis is  $\alpha = 0.0499$  (two-sided test).

If the unblinded analysis is not performed the Type 1 error probability for the final analysis will remain at  $\alpha = 0.05$  (two-sided test).

## **10 DATA QUALITY ASSURANCE**

### **10.1 Case Report Forms**

Clinical data will be entered on CRFs for transmission to the Sponsor or their designee. Data on CRFs must correspond to and be supported by source documentation maintained at the study center. All study forms and records transmitted to the Sponsor or their designee must carry only coded identifiers such that personally identifying information is not transmitted.

Any changes made to data after collection will be made through the use of Data Clarification Forms (DCF). Data reported on the CRFs, which are derived from source documents, should be consistent with the source documents or the discrepancies should be explained. CRFs will be considered complete when all missing and/or incorrect data have been resolved.

